Table 1. A visual representation of the four methods of determining apnea heart rate (HR) in beats per minute and mean arterial pressure (MAP) in mmHg. The single nadir beat (NADIR for HR) or peak beat (PEAK for MAP) is enlarged and bolded. The average of two beats (AVG2) includes the NADIR/PEAK beat and the preceding beat, underlined. The average of five beats (AVG5) includes the NADIR/PEAK beat and the four closest beats, shown in red text. The average of the five final beats (AVG_END) is shown highlighted in yellow.

	Cardiac Cycle										
	-10	-9	-8	-7	-6	-5	-4	-3	-2	-1	0
HR	71	70	66	64	59	54	51	53	52	55	54
MAP	86	85	88	87	86	90	89*	92*	96	94	97

HR: NADIR=51, AVG2=52.5, AVG5=53.8 AVG_END=53
MAP: PEAK=97, AVG2=95.5, AVG5=93.6, AVG_END=93.6
>Note: in any instance where the NADIR/PEAK beat occurs at beat 0, -1, -9 or -10 the AVG2 and/or AVG5 calculations are shifted such that only beats -10 to 0 are included in any calculations. If two beats in the final 10 cardiac cycles of an apnea are tied for NADIR/PEAK, the beat closest to the end of the apnea will be used.

4.2 Statistical Methods

We will report all continuous data as mean \pm standard deviation; modified Borg ratings will be reported as median (interquartile range). We will complete all statistical analyses in R Statistical Software (v4.3.1 R Core Team 2023). We will use summary statistics alongside boxplots and histograms to confirm the normality of continuous data. To assess absolute repeatability, we will compute within-subject standard deviations (WSSD) for heart rate, mean arterial pressure, peripheral oxygen saturation, and minute ventilation. The WSSD is the average amount we can expect an individual's future score to deviate from their current score. It is computed using a two-way ANOVA with the participant and apnea number (i.e., the identity of the apnea in a sequence of repeated measurements) as factors. The WSSD is the square root of the mean square of residuals (Hopkins, 2000; Weir, 2005). We will also calculate two-way mixed effects, absolute agreement, single measurement intraclass correlations (ICC) for heart rate, mean arterial pressure, peripheral oxygen saturation, and minute ventilation (Koo & Li, 2016). We will present all arrhythmia data as summary statistics and average percent incidence within individuals. We will present modified Borg data as summary statistics. Because none of our analyses will utilize p values or rely on the outcome of a null hypothesis test *per se*, we do not have an *a priori* alpha for statistical significance.

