2.1 Objectives

The primary objective of this study is to determine the degree of repeatability (i.e., consistency within a testing session) and reproducibility (i.e., consistency between testing sessions) of heart rate and blood pressure responses to apneas. This study also aims to determine the nature of inconsistency in these cardiovascular responses to apneas; we will ascertain whether inconsistency stems from random variability or systematic changes with repeated apneas.

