2.2. Hypotheses

We hypothesize that heart rate responses to apneas are repeatable (within-subject standard deviation [WSSD] <5 bpm; see Section 4.2 below for further details) and that greater temporal space between apneas will increase the WSSD. We also hypothesize that blood pressure responses to apneas are repeatable (WSSD <4 mmHg). Additionally, we hypothesize that inconsistency between apneas will primarily stem from random variability.

3 Participants and Methods

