Finally, participants will perform five successive test apneas, each after a five-minute hypoxic stimulus. Apnea duration for all five test apneas will correspond to the same duration as the longest of the two maximal apneas. Participants will see a live stopwatch so they are aware of the remaining duration of their apneas. They will be instructed prior to the test apneas to hold their breath for the pre-specified duration to their best ability. Participants will get at least five minutes' rest between the end of the prior apnea and the beginning of the subsequent hypoxic period. Participants will only proceed to a hypoxic period once heart rate and mean arterial pressure return to within five units of their baseline values.

On the second testing day, the maximal apneas will be used only for a measure of improvement from the first day. The test apneas on the second testing day will use the same standardized time as determined on the first testing day. On the second day we will also set the end-tidal partial pressure of carbon dioxide to the baseline value from the first day; this will eliminate any differential effects of carbon dioxide on day-to-day reproducibility.

[figure not shown]

Figure 1. Protocol schematic. Participants will begin with a vital capacity test and instrumentation. They will then complete a warm-up apnea. The hourglass and symbol above refer to whether the participant will see their apnea duration in live time. Next, participants will complete two maximal apneas; the longest apnea duration will be the time used for the five test apneas. Participants will complete the same in-lab protocol on consecutive days. On the second day the protocol is the same except participants do not complete another vital capacity test, and the test apnea time is the same as the first day, regardless of the maximal apnea times. *SpO2* peripheral oxygen saturation, *ECG* electrocardiogram, *BP* blood pressure, *AirForce* refers to the dynamic end-tidal forcing system.

Rating	Descriptor
0	Rest
1	Very, Very Easy
2	Easy
3	Moderate
4	Somewhat Hard
5	Hard
6	.
7	Very Hard
8	.
9	.
10	Maximal

Figure 2. Modified Borg scale for rating of perceived exertion. Reproduced from Foster et al. (2001).

Apnea Procedure

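### Section 4.2 misdescribes the WSSD, which excludes common drift, and no named output answers the random-versus-systematic aim

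*Combined protocol and SAP*

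**What the plan says.** **The metric.** Section 4.2 explains the WSSD in words: "The WSSD is the average amount we can expect an individual's future score to deviate from their current score". It then gives the computation: "It is computed using a two-way ANOVA with the participant and apnea number" as factors, and "The WSSD is the square root of the mean square of residuals". Section 2.2 sets the repeatability thresholds at a WSSD below 5 bpm for heart rate and below 4 mmHg for blood pressure. For the meaning of the WSSD it sends the reader onward: "see Section 4.2 below for further details".

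**The aim.** Section 2.1 states that "we will ascertain whether inconsistency stems from random variability or systematic changes with repeated apneas". Section 2.2 predicts that "inconsistency between apneas will primarily stem from random variability".

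**The outputs.** For heart rate and mean arterial pressure, Section 4.2 names the WSSD, a single-measurement absolute-agreement ICC, and a general promise to give continuous data as mean and SD. It adds that "none of our analyses will utilize p values or rely on the outcome of a null hypothesis test". Apnea number appears only as a factor in the ANOVA that yields the WSSD. Section 4.1 plans each apnea's change from free breathing. The only comparison over time that is described is in Section 3.3.2, for day 2: "the maximal apneas will be used only for a measure of improvement from the first day". That concerns the maximal apneas, not the test apneas.

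**The concern.** There are two linked problems.

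First, the verbal definition does not describe the number computed. A residual SD describes one score around its expected value. A future score compared with a current score carries error from both, so the typical gap is larger than the WSSD. Section 2.2 points readers to this definition, so they would take 5 bpm as the average gap between two apneas, which is too small.

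Second, and more important, apnea number is a factor in the ANOVA, so any shift shared by all participants leaves the residual. A response that falls or rises steadily over the session could still satisfy the WSSD threshold and be called repeatable. The study sets out to detect exactly that kind of inconsistency, yet no named output isolates it, and nothing says what would count as *primarily* random. That yardstick could be chosen after the data are seen.

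**Working it through.** **Inputs.** Thresholds of 5 bpm and 4 mmHg (Section 2.2). n = 16, m = 4 and uncertainty 0.20 (Section 4.3). Two-way ANOVA (Section 4.2). The documents give no between-participant SD and no drift, so the values used below for these are assumptions.

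**The plan's own figure.** n = 1.96² / (2 × 3 × 0.20²) = 3.8416 / 0.24 = 16.007, which agrees with the stated 16. The WSSD cancels, so nothing below affects the sample size.

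**Gap between two scores** (independent normal errors, no drift):
- SD of the difference = √2 × WSSD: 7.07 bpm or 5.66 mmHg.
- Mean absolute difference = (2/√π) × WSSD = 1.128 × WSSD: 5.64 bpm or 4.51 mmHg.
- 95% limit = 1.96 × √2 × WSSD = 2.772 × WSSD: 13.9 bpm or 11.1 mmHg.

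The stated meaning is therefore 1 − 1/1.128 = 11% too small for the average difference. Common drift widens the gap further. At residual SD 5 bpm with an assumed drift of 3 bpm per apnea, the mean absolute difference over all pairs of four apneas is 7.2 bpm, and about 12% of pairs differ by more than 13.9 bpm.

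**What the named indices show under drift** (simulated sessions, n = 16, m = 4, true error SD 5, assumed between-participant SD 8, linear drift):

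| Total drift over four apneas (bpm) | WSSD as planned | Within-subject SD that keeps drift | Absolute-agreement ICC |
|---|---|---|---|
| 0 | 5.00 | 5.00 | 0.70 |
| −6 | 5.00 | 5.63 | 0.65 |
| −12 | 4.98 | 7.18 | 0.53 |

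In the last row the apnea means 0, −4, −8, −12 have variance (36 + 4 + 4 + 36)/3 = 26.7, against a residual variance of 25. The systematic share is 26.7/51.7 = 52%, yet the WSSD has not moved. The ICC falls, but by itself it cannot say why. In expectation it is about 64/(64 + 25 + 26.7) = 0.55, and a session with no drift and a residual variance of 51.7 gives the same value.

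**The residual is not purely random either.** With one score per participant per apnea, the residual also holds participant-specific trends. With error SD 4.5 and individual slopes of SD 2 bpm per apnea (assumed, mean zero), the residual variance is 4.5² + 2² × 5/3 = 20.25 + 6.67 = 26.9, so the WSSD is 5.19.

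**Can the planned data answer the question?** Yes, for mean changes. With 45 residual df, t = 2.014. The 95% CI half-width for a change between two apnea means is 2.014 × WSSD × √(2/16): 3.56 bpm at WSSD 5 and 2.85 mmHg at WSSD 4. The variance component is less precise. At residual SD 4.5 and drift 3 bpm per apnea, the true share is 15/(15 + 20.25) = 0.43, and the middle 95% of simulated estimates run from 0.22 to 0.61.

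**The case against.** **The exact formula is there.** It follows the loose sentence closely, and no computation, threshold or sample size depends on the wording. That is correct. Taken alone, the definition is a wording fault of about 11%. A reader might infer that the analysis or the sample size is invalid, and the documents do not support that.

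**Means and SDs are promised.** Section 4.2 gives mean and SD for all continuous data, and in a repeated-apnea study means by apnea are a natural reading. On that reading the direction of drift would be visible. The systematic variance could then be worked back as (V − WSSD²)/ICC − V, with V the mean per-apnea variance. This objection has force: it would be too strong to say that the plan can produce no result for the aim. But the sentence does not say by apnea number or by session. Between-participant SDs give no interval for a within-participant change, and no rule for *primarily* follows from them.

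**The ANOVA already contains the factor.** It does, but only as a step towards the WSSD. This makes the remedy cheap; it does not supply the missing output.

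**Change is already measured.** Section 4.1 takes change from free breathing within each apnea, and the day-to-day improvement measure uses the maximal apneas. Neither is a change across the test apneas.

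**Conclusion.** The point holds and should be corrected before analysis. The verbal definition describes a different quantity from the one computed. At the thresholds, the average gap between two scores is 5.64 bpm or 4.51 mmHg and the 95% limit is 13.9 bpm or 11.1 mmHg, given independent normal errors and no drift. The larger matter is that the WSSD excludes common drift by construction and the ICC blends it with random error. Repeatability could therefore be declared alongside a large order effect, and the named outputs do not separate the two.

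Two further inferences are not supported. The documents give no drift figure, so nothing here says that drift will occur or how large it will be; the 12 bpm case is illustrative. Nor may the WSSD be described as random error alone, because participant-specific trends stay in the residual.

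**What to change.** 1. **Definition.** Describe the WSSD as the SD of a single score about its expected value, net of the common apnea-number effect. Report 2.77 × WSSD beside it. State that the 5 bpm and 4 mmHg thresholds exclude common drift but include participant-specific trends.
2. **Output.** From the planned ANOVA, report the test-apnea mean changes by apnea number with 95% CIs for each session. Also report the day 1 to day 2 mean change in the test apneas with its 95% CI. No p value is needed, so this respects Section 4.2. Where the fifth apnea is substituted under Section 4.3, keep it at its true position in the sequence.
3. **Criterion.** State in advance how *primarily* random will be judged, on a measure that uses all the apnea means. One option is the apnea-number variance component, (MS_apnea − MS_residual)/n, shown beside the residual variance with its uncertainty. Do not rely on the first-to-fourth change alone. Apnea means of 0, −10, −10, 0 at residual SD 5 have a systematic share of 33.3/(33.3 + 25) = 57%. A rule that compared only the first-to-fourth change with 2.32 × WSSD (the point where linear drift equals random variance) read this pattern as mainly random in over 99.9% of simulated sessions.

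**Cost.** SAP wording and a few more reported numbers; no new data or participants. The variance share will be imprecise at n = 16. Keeping substituted apneas in position widens some intervals. If 4 of 16 participants use the fifth apnea, the half-widths against apnea 1 at WSSD 5 rise from 3.56 to 3.71 bpm for apneas 2 to 4, and the half-width for apnea 5 is 6.25 bpm.

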4.3 Sample Size Determination

We will recruit 20 participants to ensure we obtain 16 participants who reach their target apnea time on at least 4 of the 5 test apneas on both test days. McAlinden et al. (2015) presented a method for calculating sample size for a repeatability and reproducibility study:

$$1.96 \frac{WSSD}{\sqrt{2n(m-1)}} = WSSD \times LC$$

where n is the sample size, m is the number of repeated measurements, and LC is the desired level of uncertainty between the sample WSSD and the population parameter. Note that WSSD appears on both sides of the equation and therefore divides to one; in other words, the magnitude of the WSSD does not affect the sample size calculation. Rearranging the equation to isolate n , using 20% uncertainty between the sample estimate and the population parameter ($LC = 0.20$), and four repeated trials ($m = 4$), we require 16 participants. Therefore, to account for instrumental challenges and incomplete trials we will recruit up to 20 participants to obtain a complete sample of eight males and eight females who will complete five apneas per trial. If all apneas go well then we will analyze the first four and discard the final apnea; we decided *a priori* that we will only use the final apnea for analysis if an apnea duration deviates more than two seconds from the target time, or if the heart rhythm is uninterpretable during analysis from excessive participant movement or any other cause. We will record and report every instance that we use the final apnea for analysis, and the reason for its use.

5 References

Busch, S. A., Davies, H., van Diepen, S., Simpson, L. L., Sobierajski, F., Riske, L., Stembridge, M., Ainslie, P. N., Willie, C. K., Hoiland, R., Moore, J. P., & Steinback, C. D. (2018). Chemoreflex mediated arrhythmia during apnea at 5,050 m in low- but not high-altitude natives. *Journal of Applied Physiology*, 124(4), 930–937. <https://doi.org/10.1152/japplphysiol.00774.2017>

Busch, S. A., van Diepen, S., Roberts, R., Steele, A. R., Berthelsen, L. F., Smorschok, M. P., Bourgoin, C., & Steinback, C. D. (2021). Short-term hypoxia does not promote arrhythmia during voluntary apnea. *Physiological Reports*, 9(1), e14703. <https://doi.org/10.14814/phy2.14703>

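### Section 4.3 claims 20% uncertainty from 48 degrees of freedom, but the two-way ANOVA in 4.2 leaves 45 within a session, so the figure is about 20.7%: a minor mismatch that does not invalidate the sample size

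*Combined protocol and SAP*

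**What the plan says.** Section 4.3 sizes the study on the precision of the WSSD. It sets 1.96·WSSD/√(2n(m-1)) equal to WSSD·LC, takes LC = 0.20 ("using 20% uncertainty between the sample estimate and the population parameter"), "and four repeated trials ($m = 4$), we require 16 participants". Five apneas are performed per session, but the fifth is a reserve: "If all apneas go well then we will analyze the first four and discard the final apnea". Recruitment allows for losses: "we will recruit up to 20 participants to obtain a complete sample of eight males and eight females".

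Section 4.2 defines the quantity being estimated. Of the WSSD it says "It is computed using a two-way ANOVA with the participant and apnea number" as factors, and "The WSSD is the square root of the mean square of residuals". It plans no p values and sets no alpha. It gives no interval method for the WSSD, and it does not say whether the two days are analysed separately or together.

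Section 2.1 defines repeatability as consistency within a session. Section 2.2 hypothesises a WSSD below 5 bpm for heart rate and below 4 mmHg for blood pressure.

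**The concern.** The term n(m-1) in the 4.3 formula is the residual df of an ANOVA with participant as the only factor. The model in 4.2 has a second factor, apnea number, which uses a further m-1 df. The sample size therefore rests on a slightly different model from the one to be fitted, and neither section mentions the difference. Because the plan uses no hypothesis test, this precision figure is the only justification given for 16 participants, so it should match the planned analysis.

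A second, separate issue is how the 20% will be read. The hypotheses in 2.2 put upper bounds on the WSSD, so a reader will want to know how far the population value could lie above the estimate. A symmetric percentage understates that side.

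**Working it through.** **Inputs.** LC = 0.20, m = 4, n = 16 and the multiplier 1.96 (section 4.3); additive two-way ANOVA with participant and apnea number (section 4.2); one session at a time (an assumption, consistent with m = 4 and with the definition of repeatability in 2.1).

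**1. Reproduce the plan's figure.** Solving the 4.3 formula for n:

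n = 1.96² / (2 × 3 × 0.20²) = 3.8416 / 0.24 = 16.007, stated as 16.

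At n = 16, df = 16 × 3 = 48 and LC = 1.96/√96 = 20.00%. The plan's arithmetic is right for its own formula.

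**2. Residual df of the planned model.** With 16 × 4 = 64 observations: 64 - 1 - 15 (participants) - 3 (apnea number) = 45 = (n-1)(m-1).

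**3. Same formula, planned df.** LC = 1.96/√(2 × 45) = 1.96/√90 = 20.66%, which is 0.66 percentage points above the stated 20%.

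**4. Completers needed for 20%.** Setting (n-1)(m-1) in place of n(m-1) gives n = 1 + 16.007 = 17.007. With the plan's own rounding that is 17 (df 48, LC 20.00%). Strict rounding up gives 18 (df 51, LC 19.4%).

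**5. Exact 95% limits.** For the population WSSD relative to the estimate, the limits are √(df/χ²₀.₉₇₅) - 1 and √(df/χ²₀.₀₂₅) - 1:

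| df | Normal approximation | Exact lower | Exact upper |
|---|---|---|---|
| 48 (formula in 4.3) | ±20.0% | -16.6% | +24.9% |
| 45 (model in 4.2) | ±20.7% | -17.1% | +26.0% |

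Of the roughly 6 points between +20% and +26%, about 5 are already present at 48 df and about 1 comes from the lost df.

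**6. Against the hypotheses.** Under a symmetric 20% margin, an estimate would sit clear of the bound up to 5/1.20 = 4.17 bpm or 4/1.20 = 3.33 mmHg. With the exact upper limit at 45 df the values are 5/1.2595 = 3.97 bpm and 4/1.2595 = 3.18 mmHg. As an illustration only, an assumed estimate of 4.5 bpm would have an exact interval of 3.7 to 5.7 bpm.

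**7. Sensitivity to what 4.2 leaves open.**
- Both days pooled (assumption): two separate session models give 2 × 45 = 90 df and 14.6%; one model with eight apneas gives 15 × 7 = 105 df and 13.5%.
- A reserve apnea keeping its own sequence number (assumption): five levels, 64 - 1 - 15 - 4 = 44 df, and 1.96/√88 = 20.9%.
- All 20 recruits analysable in one session: 19 × 3 = 57 df and 18.4%.

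**The case against.** The strongest reply is that the effect is negligible. LC = 0.20 is a round planning choice, the stated 16 follows from the stated formula, one more completer restores 20.0%, and up to 20 are recruited. All of this stands, and no design decision changes. It does not remove the mismatch: the plan quotes its precision for 16 completers, and the further four are there to cover losses.

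A second reply is that 45 df is not fixed by the documents, because 4.2 is silent on pooling the two days. This also stands, and the 20.7% must carry that condition. The use of m = 4 in 4.3 and the within-session definition in 2.1 support the per-session reading.

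A third reply is that the 20% is fair as a statement of how the estimate scatters around the true value: at 48 df the exact 95% range for that is -20.0% to +19.9%. That is correct. The asymmetry appears when the statement is turned round into limits for the population WSSD given the estimate, which is what a reader needs for the hypotheses in 2.2.

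A reader might also infer that +26% instead of +20% results from the df mismatch. It does not, since the plan's own 48 df already gives +24.9%. Nor do the documents require an upper confidence limit to fall below 5 bpm or 4 mmHg; section 2.2 states the bounds without any such criterion.

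**Conclusion.** The point holds as a minor inconsistency between 4.2 and 4.3. For 16 completers, four analysed apneas each and sessions analysed separately, the plan's own formula gives about 20.7%, not 20.0%, and the shortfall is worth one participant. The conclusion rests on a balanced additive model within one session; pooling both days would give more df and a figure below 20%.

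The upper-side understatement is a separate matter. It comes mainly from using a symmetric normal approximation and would remain with the 48 df in 4.3.

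It would be tempting to conclude that the sample size is wrong or that the study cannot meet its aim. The documents do not support that: the calculation in 4.3 reproduces, the difference is 0.66 percentage points, and recruitment runs to 20.

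**What to change.** Keep 16 participants.

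- In 4.3, restate the expected 95% uncertainty as about 21% per session, based on 45 residual df (exact chi-square limits -17% to +26%). State that this assumes each session is analysed separately, and that pooling both days would give more df and a smaller figure.
- In 4.2, add that each WSSD is reported with its exact chi-square 95% interval, using the residual df of the model actually fitted, so that it can be read against the hypotheses of <5 bpm and <4 mmHg.

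The cost is one sentence in 4.3, one added analysis output in 4.2, and a slightly less favourable stated precision. No participants or procedures are added.

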3.3.3 Measurements

Respiratory Measures:

Figure 3 shows a schematic of the mouthpiece setup. Participants will wear a nose clip and breathe through a mouthpiece attached to a pneumotachometer (MLT3813H-V, ADInstruments) and a 3-way non-rebreathing valve (T-Shape Series, 2700, Hans Rudolph). The inspired port of the valve will connect to a dynamic end-tidal forcing system that will control end-tidal oxygen and carbon dioxide on a breath-by-breath basis using offline software (Labview 16.0, National Instruments). The mouthpiece will have a small sampling port connected to oxygen (S-3A/I Oxygen Analyzer & Model N-22M Sensor, AEI Technologies) and carbon dioxide (CD-3A Carbon Dioxide Analyzer & P-61B Sensor, AEI Technologies) gas analyzers run in parallel. The gas analyzer user manual claims accuracy within $\pm 0.01\%$ O₂ and $\pm 0.02\%$ CO₂ (“Respiratory Gas Analyzers,” n.d.). The gas analyzer delays will be measured daily in accordance with the calibration procedures for the dynamic end-tidal forcing system. A respiratory strain gauge (Model TN1132/ST, ADInstruments) placed around the chest will measure respiratory movements during normal breathing and breath-holding and will assist in detecting the end of each apnea.

Cardiovascular Measures:

We will measure heart rate and rhythm using an electrocardiogram (lead II). We will measure blood pressure using finger photoplethysmography (Finometer Pro, Finapres Medical Systems) calibrated to manual blood pressure measurements taken in triplicate during the baseline. We will measure peripheral hemoglobin oxygen saturation using pulse oximetry (Nellcor N-600x, Medtronics).

Borg Scale:

We will ask participants to rate the effort of each test apnea on a scale of 1-10. We will also have a visual modified Borg scale diagram to assist participants in rating the effort of each apnea (Figure 2).

4 Statistical Analysis Plan

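### The rule for using the spare fifth apnea has no trigger for an unusable blood pressure trace, and completers are counted by apnea time alone

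*Combined protocol and SAP*

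**What the plan says.** Section 4.3 fixes in advance when the fifth test apnea enters the analysis. The default is "If all apneas go well then we will analyze the first four and discard the final apnea". The exceptions form a closed list of two. The first concerns timing: "we will only use the final apnea for analysis if an apnea duration deviates more than two seconds from the target time". The second concerns the ECG and reads "or if the heart rhythm is uninterpretable during analysis from excessive participant movement or any other cause". Each use of the fifth apnea, with its reason, is to be recorded and reported.

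The recruitment target in the same section is "16 participants who reach their target apnea time on at least 4 of the 5 test apneas on both test days". That definition refers to time only. The margin is stated as "to account for instrumental challenges and incomplete trials we will recruit up to 20 participants".

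Section 2.1 puts heart rate and blood pressure side by side in the primary objective, and Section 2.2 gives blood pressure its own limit, a within-subject standard deviation (WSSD) below 4 mmHg. On the instruments, Section 3.3.3 says "We will measure blood pressure using finger photoplethysmography", whereas heart rate and rhythm come from a lead II electrocardiogram. Section 4.2 computes a WSSD and an intraclass correlation (ICC) for MAP, with apnea number as an ANOVA factor. No section says what happens when a pressure trace is unusable or a MAP value is missing.

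**The concern.** The two triggers protect the heart rate analysis but not the MAP analysis. Suppose apnea 3 lasts the target time and has a readable ECG, but the finger pressure is lost in the final 10 cardiac cycles, where the apnea values are taken. Neither trigger applies. Apnea 3 stays in the analysed four without a usable MAP value, and a sound fifth apnea is set aside. This is more than missing detail: followed as written, the rule discards usable data on a primary response.

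The completer count has a related gap, which also touches heart rate. Take a participant who misses the target time on one apnea and has an unreadable ECG or pressure trace on another. Target time was reached on four of five, so this participant is one of the 16. For the affected outcome only three apneas can be analysed. The spare cannot repair this case, because one apnea is already lost to the duration miss; only the definition of a completer can.

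At stake is whether the MAP result has the precision that Section 4.3 was sized for. Using the fifth apnea for MAP after the data are seen would be an unplanned choice on a primary response.

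**Working it through.** **Inputs from Section 4.3:** LC = 0.20, m = 4 apneas per session, n = 16, five apneas performed. **Assumed:** each pressure trace is lost independently with probability q = 2%, 5% or 10%, and the spare has not been used for a duration miss. The documents give no loss rate.

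**1. The plan's own figure.** Rearranged, n = (1.96/LC)² / (2(m − 1)) = (1.96/0.20)² / 6 = 96.04/6 = 16.007, which reproduces 16. Conversely, LC = 1.96/√(2 × 16 × 3) = 1.96/√96 = 20.0%. There is no slack at 16.

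**2. No replacement, all available MAP values analysed.** Replace n(m − 1) by its expected value, 16 × (4(1 − q) − 1):
- q = 2%: 16 × 2.92 = 46.72; 1.96/√93.44 = 20.3%
- q = 5%: 16 × 2.80 = 44.80; 1.96/√89.60 = 20.7%
- q = 10%: 16 × 2.60 = 41.60; 1.96/√83.20 = 21.5%

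**3. Fifth apnea allowed, all available values analysed.** The number of usable apneas is the smaller of 4 and a binomial count out of 5 with success probability 1 − q:
- q = 2%: mean 3.996; 16 × 2.996 = 47.94; 1.96/√95.87 = 20.0%
- q = 5%: mean 3.976; 16 × 2.976 = 47.62; 1.96/√95.24 = 20.1%
- q = 10%: mean 3.910; 16 × 2.910 = 46.55; 1.96/√93.10 = 20.3%

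**4. If participants with a missing value were dropped (one session, q = 5%).** Without replacement, 16 × 0.95⁴ = 13.03 remain, so about 3.0 are lost, and 1.96/√(6 × 13.03) = 22.2%. With the spare, 16 × P(at least 4 of 5 usable) = 15.64 remain, and 1.96/√(6 × 15.64) = 20.2%.

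**5. The completer gap.** One participant with three analysable apneas instead of four takes n(m − 1) from 48 to 47: 1.96/√94 = 20.2%. If four participants were affected, it would be 44: 1.96/√88 = 20.9%.

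**The case against.** **The wording could be read generously.** The phrase about any other cause, and the condition that all apneas go well, might seem to cover a lost pressure trace. But the first explains why a heart rhythm is uninterpretable, and the second is followed by a closed list introduced by the word only.

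**The plan already allows for instrument failure.** Recruiting up to 20 to obtain 16 is a stated margin, and Section 4.3 speaks of a complete sample of eight men and eight women. That is a fair point at the level of participants. It does not permit an apnea to be replaced, and the stated criterion, participants "who reach their target apnea time on at least 4 of the 5 test apneas on both test days", still counts someone whose pressure traces were lost.

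**The loss of precision is small.** This stands. A residual mean square can be computed with missing cells, and nothing in Section 4.2 says that incomplete participants are dropped. The 22.2% figure is therefore a conditional case, not the plan's consequence.

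**The benefit of the spare is uncertain.** This also stands. If losses cluster within a participant, fewer participants are affected and the fifth trace is often lost too. The test apneas are held to the participant's own longest maximal time, so the spare may already be needed for a duration miss.

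**One common set of four apneas has merit.** It ties heart rate, MAP and saturation to the same events. Apnea order also matters, because Section 2.1 asks about systematic change with repetition. Any change has to respect that order.

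**Conclusion.** The gap is clear on the text. The fifth apnea cannot be used when only the pressure trace fails, and a completer need not have four analysable apneas for either primary response.

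Its size is modest. With all available values analysed, MAP uncertainty rises from 20.0% to between 20.3% and 21.5% over the assumed 2% to 10% loss, and use of the spare recovers most of that. The figures rest on the assumed loss rates, on independence and on an unused spare; the last two favour the spare.

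Three stronger readings are tempting, and the documents do not support them.
- A reader might require completeness on all eight apneas over both days. At 5% loss this leaves 16 × 0.95⁸ = 10.61 participants, and m = 4 then gives 1.96/√(6 × 10.61) = 24.6%. But a single-session WSSD does not need the other day's data, and pooling both days would mean m = 8 and 1.96/√(14 × 10.61) = 16.1%. The 24.6% matches no analysis stated in the plan.
- A reader might infer that artefact will inflate the MAP WSSD through the single peak beat. The documents give no figure for this and do not say that artefactual beats would be kept. Section 4.1 also defines three averaged measures alongside the single-beat one.
- A reader might conclude that the sample is too small because m = 3 needs 96.04/4 = 24.01 participants, more than the 20 to be recruited. That would require every participant to lose an apnea.

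The change is worth making because it is nearly free, not because the sample size fails.

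**What to change.** In Section 4.3:
1. Add an unusable finger-pressure waveform in the final 10 cardiac cycles as a trigger for using the fifth apnea in the MAP analysis. Keep the duration trigger for both responses and the heart rhythm trigger for heart rate.
2. Judge waveform usability before any WSSD is computed, and log each use with the spare uses already to be reported.
3. Keep the replacement's true sequence number (apnea 5) in the ANOVA; do not relabel it as the apnea it replaces.
4. Count a completer, for each outcome, as having at least four on-target apneas per day with an analysable signal for that outcome.

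State also whether participants with a missing MAP value stay in the analysis, since that decides which figures above apply.

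**Cost.** A few sentences and no new measurement, because five test apneas are already scheduled. Heart rate and MAP may occasionally come from different apneas of a session, and slightly fewer recruits may count as completers. Treating apnea 5 as a separate factor level also uses one residual degree of freedom, which the plan's formula does not count. If only one participant has an apnea 5 value in a session, that value adds nothing to the residual. At 5% loss, deducting one from 47.62 gives 1.96/√(2 × 46.62) = 20.3% instead of 20.1%.
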